9.4.2 Clinical Laboratory

The raw values and change from baseline values of the continuous hematology, chemistry, and coagulation parameters will be summarized in SI units by treatment group at each scheduled time point during the TE period.

The number and percentage of subjects with at least 1 potentially clinically significant (PCS) event during the TE period will be summarized overall and by treatment group. The PCS criteria are provided in [Appendix E](#).

Immunogenicity analysis is out of the scope of this SAP.

Results of urinalysis and the serum pregnancy test will be listed in individual subject data listings only.

A listing of subjects with elevated liver function results (defined as any of the following: $AST \geq 3 \times ULN$, $ALT \geq 3 \times ULN$, $ALP \geq 1.5 \times ULN$, or total bilirubin $\geq 2 \times ULN$) during the TE period will be presented. For each subject in the listing, LFT assessments at all visits will be included.

In addition, listings containing individual subject laboratory assessment values outside the reference ranges will be provided. Individual subject data listings will include data from scheduled and unscheduled time points.

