8.1 Overview of Study Design

This is a multicenter, randomized, double-blind, placebo-controlled study to examine the efficacy and safety of VX-210 treatment. The study will be conducted at approximately 45 sites in the United States and Canada and will enroll approximately 100 male or female subjects 14 to 75 years of age (inclusive) with acute traumatic SCI, C4 to C7 (motor level) on each side, and AIS grade A or AIS grade B. Subjects will be randomized to receive a single 9-mg dose of VX-210 in fibrin sealant or a placebo (buffer solution) in fibrin sealant at a 1:1 ratio until approximately 100 subjects are enrolled (approximately 50 subjects in each treatment arm: 9-mg VX-210 and placebo). Subjects will be stratified by age (<30 versus \geq 30 years of age) and AIS grade (A versus B with sacral pinprick preservation versus B without sacral pinprick preservation) when they are randomized to the 2 study arms. The 1-time dose of VX-210 or placebo will be administered by a surgeon directly to the dura mater of the spinal cord at the site of injury during decompression/stabilization surgery that commences within 72 hours after the initial injury.

For an individual subject, the study will last approximately 12 months. Follow-up appointments after the initial hospital stay will be at 6 weeks, 3 months, 6 months, and 12 months after treatment. At specified time points during the study, subjects will be evaluated for medical, neurological, and functional changes, and serum will be collected for PK and immunological analyses (Table 3-1).

A schematic of the study design is provided in Figure 8-1.

Figure 8-1 Schematic of Study Design

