11.6.2 Clinical Laboratory Assessments

Blood and urine samples for safety assessment will be analyzed at each site's local laboratory. See the following sections for details regarding collection of blood samples for immunogenicity (Section 11.6.6), PK (Section 11.3).

Blood samples for clinical laboratory assessments will be collected at time points indicated in Table 3-1. After screening, laboratory test results that are abnormal and considered clinically significant will be reported as AEs (see Section 13.1).

The safety laboratory test panels are shown in Table 11-1.

Table 11-1 Safety Laboratory Test Panels

Serum Chemistry	Hematology	Urinalysis
Glucose	Hemoglobin	Leukocyte esterase
Blood urea nitrogen	Erythrocytes	Nitrite
Creatinine	Mean corpuscular hemoglobin	Urobilinogen
Sodium	Mean corpuscular hemoglobin concentration	Urine protein
Potassium	Mean corpuscular volume	pH
Calcium	Platelets	Urine blood
Chloride	Leukocytes	Specific gravity
Magnesium	Differential (absolute and percent):	Urine ketones
Bicarbonate	Eosinophils	Urine bilirubin
Inorganic phosphate	Basophils	Urine glucose
Total bilirubin, direct bilirubin	Neutrophils	
Alkaline phosphatase	Lymphocytes	
Aspartate aminotransferase (= SGOT)	Monocytes	
Alanine aminotransferase (= SGPT)	Coagulation Studies	
Amylase	Activated partial thromboplastin time	
Lipase	Prothrombin time	
Gamma glutamyl transferase	Prothrombin time International Normalized Ratio	
Total protein		
Albumin		
Creatine kinase .		
Uric acid		
Cholesterol		

Table 11-1 Safety Laboratory Test Panels

Serum Chemistry	Hematology	Urinalysis
Triglycerides Low-density lipoprotein High-density lipoprotein		

Additional tests at screening: The following additional tests will be performed during screening to assess eligibility or contraception requirements:

- Serum beta-human chorionic gonadotropin (BHCG) for all female subjects
- Serum follicle-stimulating hormone (FSH) for suspected postmenopausal female subjects <60 years of age when a waiver to contraception is sought. Levels will be within the laboratory's range for postmenopausal for subjects to be considered of non-childbearing potential.

Clinical laboratory assessments from screening will have no clinically significant findings that preclude participation in the study, as judged by the investigator, for a subject to receive study drug.

Additional Evaluations: Additional clinical laboratory evaluations will be performed at other times if judged to be clinically appropriate.

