12.3.1 General Considerations

All individual subject data for all individual subjects randomized or received study drug will be presented in data listings.

Continuous variables will be summarized using the following descriptive summary statistics: the number of subjects (n), mean, SD, standard error (SE), median, minimum value (min), and maximum value (max). The precision of the measurement for each continuous variable will be used to determine the number of decimal places to present in tables, figures, and derived listings. Unless otherwise specified, min and max values will be reported with the same precision as the units of measure; the mean, median, SD, and SE will be reported to 1 greater decimal place. Any values that require transformation to standard units (metric or International System [SI]) will be converted with the appropriate corresponding precision. Details will be provided in the SAP.

Categorical variables will be summarized using counts and percentages. Percentages will be presented to 1 decimal place.

Baseline value, unless otherwise specified, will be defined as the most recent non-missing measurement (scheduled or unscheduled) collected before administration of study drug.

Change (absolute change) from baseline will be calculated as postbaseline value - baseline value.

The treatment-emergent (TE) period will include the time from dosing with study drug to the Safety Follow-up Visit or 28 days after treatment for subjects who do not have a Safety Follow-up Visit.

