7 STUDY DESIGN

7.1 Overall Design

[figure not shown]
This is a multicenter, randomized, double-blind, placebo-controlled study to examine the efficacy and safety of VX-210 treatment. The study will be conducted at approximately 45 sites in the United States and Canada and will enroll approximately 100 male or female subjects 14 to 75 years of age (inclusive) with acute traumatic SCI, C4 to C7 (motor level) on each side, and AIS grade A or AIS grade B. Subjects will be randomized to receive a single 9-mg dose of VX-210 in fibrin sealant or a placebo (buffer solution) in fibrin sealant at a 1:1 ratio until approximately 100 subjects are enrolled (approximately 50 subjects in each treatment arm: 9-mg VX-210 and placebo). Subjects will be stratified by age (<30 versus ≥30 years of age) and AIS grade (A versus B with sacral pinprick preservation versus B without sacral pinprick preservation) when they are randomized to the 2 study arms. The 1-time dose of VX-210 or placebo will be administered by a surgeon directly to the dura mater of the spinal cord at the site of injury during decompression/stabilization surgery that commences within 72 hours after the initial injury.

For an individual subject, the study will last approximately 12 months. Follow-up appointments after the initial hospital stay will be at 6 weeks, 3 months, 6 months, and

12 months after treatment. At specified time points during the study, subjects will be evaluated for medical, neurological, and functional changes, and serum will be collected for PK and immunological analyses.

A schematic of the study design is provided in [Figure 7-1](#).

Figure 7-1 Schematic of Study Design

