Appendix E: Criteria for Potentially Clinically Significant Events

Table 12-4 Criteria for Potentially Clinically Significant Laboratory Tests

Parameter	PCS	Comments
Clinical Chemistry		
ALT	$\leq 3xULN^*$ (Not a PCS criterion) $>3x - \leq 5xULN$ $>5x - \leq 8xULN$ $>3xULN$ $>5xULN$ $>8xULN$	FDA DILI Guidance Jul 2009.
AST	$\leq 3xULN^*$ (Not a PCS criterion) $>3x - \leq 5xULN$ $>5x - \leq 8xULN$ $>3xULN$ $>5xULN$ $>8xULN$	FDA DILI Guidance Jul 2009.
ALT or AST	ALT $>3xULN$ or AST $>3xULN$	Vertex LFT working group 2014
Alkaline Phosphatase	$>1.5xULN$	FDA DILI Guidance Jul 2009.
Total Bilirubin	$>1.5x - \leq 2xULN$ $>2xULN$	FDA DILI Guidance Jul 2009.
ALT and Total Bilirubin	ALT $>3xULN$ and TBILI $>2xULN$	FDA DILI Guidance Jul 2009. To be counted within a same treatment phase, whatever the interval between measurements.
AST and Total Bilirubin	AST $>3xULN$ and TBILI $>2xULN$	FDA DILI Guidance Jul 2009. To be counted within a same treatment phase, whatever the interval between measurements.
(ALT or AST) and Total Bilirubin	(ALT $>3xULN$ or AST $>3xULN$) and TBILI $>2xULN$	Vertex LFT working group 2014
CPK	$>3x - \leq 10xULN$ $>10xULN$	FDA criteria Feb 2005. Am J Cardiol April 2006.
Creatinine	$\geq 150 \mu\text{mol/L}$ (Adults) $\geq 30\%$ change from baseline $\geq 100\%$ change from baseline	Benichou C., 1994.
Uric Acid		Harrison- Principles of internal Medicine 17th Ed., 2008.
Hypouricemia	$<120 \mu\text{mol/L}$	
Hyperuricemia	$>408 \mu\text{mol/L}$	
Blood Urea Nitrogen	$\geq 17 \text{ mmol/L}$	
Chloride	$<85 \text{ mmol/L}$ $>115 \text{ mmol/L}$	
Sodium	$\leq 129 \text{ mmol/L}$ $\geq 150 \text{ mmol/L}$	

Table 12-4 Criteria for Potentially Clinically Significant Laboratory Tests

Parameter	PCS	Comments
Potassium	<3 mmol/L ≥5.5 mmol/L	FDA Feb 2005.
Total Cholesterol	≥7.74 mmol/L	Threshold for therapeutic intervention.
Triglycerides	≥4.6 mmol/L	Threshold for therapeutic intervention.
Glucose		
Hypoglycaemia	≤3.9 mmol/L and <LLN	ADA May 2005.
Hyperglycaemia	≥11.1 mmol/L (unfasted); ≥7 mmol/L (fasted)	ADA Jan 2008.
Albumin	≤25 g/L	
Amylase	>2.0 - 5.0 x ULN >5.0 x ULN	Criteria based upon CTCAE
Lipase	>2.0 - 5.0 x ULN >5.0 x ULN	Criteria based upon CTCAE
Hematology		
WBC	<3.0 Giga/L (Non-Black); <2.0 Giga/L (Black) ≥16.0 Giga/L	Increase in WBC: not relevant. To be interpreted only if no differential count available.
Lymphocytes	<1.0 Giga/L >4.0 Giga/L	

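### SAP 9.4.2 pools local-laboratory values without scaling to local limits, which adds avoidable noise to the by-arm tables for enzymes, bilirubin and aPTT

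*SAP*

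**What the plan says.** Protocol 11.6.2 states: "Blood and urine samples for safety assessment will be analyzed at each site's local laboratory". Protocol 8.1 adds: "The study will be conducted at approximately 45 sites in the United States and Canada". SAP 7.1 plans "approximately 50 subjects in each treatment arm: 9-mg VX-210 and placebo". Randomization is 1:1, stratified by age and AIS grade and not by site (SAP 7.3).

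For the continuous tables, SAP 9.4.2 says that raw and change-from-baseline "values of the continuous hematology, chemistry, and coagulation parameters will be summarized in SI units by treatment group". This is done at each scheduled time point. Protocol 12.3.4.2 makes the same commitment. The only harmonization step is unit conversion, in Protocol 12.3.1: "Any values that require transformation to standard units (metric or International System [SI]) will be converted with the appropriate corresponding precision".

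Local limits are used elsewhere in the plan:
- SAP Table 12-4 sets the potentially clinically significant (PCS) criteria for ALT, AST, ALP, total bilirubin, CPK, amylase and lipase as multiples of ULN. For amylase and lipase they read ">2.0 - 5.0 x ULN >5.0 x ULN".
- The liver listing in SAP 9.4.2 also uses ULN, and a separate listing shows values outside the reference ranges.

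GGT is in the protocol's panel (Table 11-1) but has no PCS criterion. The PCS limits for aPTT (65 seconds) and PT (17 seconds) are absolute times. INR is in the panel and has its own PCS limit of 1.7. SAP 9.1 keeps a 3-mg group in all safety analyses, made up of subjects dosed under protocol version 1.0.

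**The concern.** The plan judges large enzyme excursions against each laboratory's own limit, but it averages the same enzymes without that correction. If two laboratories report the same sample on different scales, the pooled mean reflects the mix of laboratories as well as the subjects. With about 100 / 45 = 2.2 subjects per site and no stratification by site, that mix can differ between arms by chance.

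Safety is part of the primary objective and laboratory values are a named safety endpoint, so these tables should be as precise as the data allow. Three places have little other by-arm cover:
- **GGT:** the unscaled summary is its only by-arm summary.
- **aPTT:** its PCS limit is also unscaled.
- **ALT and AST shifts below 3×ULN:** these fall under the PCS threshold. The out-of-range listing shows such values subject by subject, but it is not a summary by arm.

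**Working it through.** The plan states no figure for laboratory variability, so there is nothing of its own to reproduce.

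**Inputs from the documents:** 100 subjects, 50 per arm, about 45 sites, 1:1 allocation not stratified by site. One laboratory per site is an inference.

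**Assumed inputs:**
- Between-laboratory CV (c) of 10%, 20% or 30%, acting as a multiplier.
- Enzyme-like test: between-subject CV 35%, within-subject CV 20%, typical value 30.
- Scaling to the local limit removes the laboratory factor completely.

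**Simulation:** 45 laboratories, 4,000 repeats per setting, no drug effect. Entries are the SD of the between-arm difference in means.

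| c | Raw value | Value scaled to local limit | Change, same laboratory | Change, 30% of baselines from another laboratory |
|---|---|---|---|---|
| 0 | 2.67 | 2.67 | 1.98 | 1.96 |
| 10% | 2.83 | 2.73 | 2.00 | 2.07 |
| 20% | 3.12 | 2.70 | 2.02 | 2.33 |
| 30% | 3.53 | 2.71 | 2.14 | 2.75 |

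- Raw against scaled in the same runs: 2.83/2.73 = 1.04, 3.12/2.70 = 1.16, 3.53/2.71 = 1.30. The rise is about 5% to 30%.
- Change, same laboratory: 2.00/1.98 = 1.01, 2.02/1.98 = 1.02, 2.14/1.98 = 1.08. The rise is about 0% to 8%.
- Change, mixed baselines: 2.07/1.96 = 1.06, 2.33/1.96 = 1.19, 2.75/1.96 = 1.40.
- The average between-arm difference lay between −0.05 and 0.06 throughout, so there is no bias.

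**Check by formula (raw).** With an independent laboratory factor of mean 1, the SD ratio is √(1 + c²(1 + 1/CV²)). The total subject CV satisfies CV² = 1.1225 × 1.04 − 1 = 0.1674, so 1 + 1/CV² = 6.97. The ratio is √1.070 = 1.03, √1.279 = 1.13 and √1.628 = 1.28. The simulation is slightly higher at 30%, mainly because its log-normal factor has a mean of exp(0.09/2) = 1.046.

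**Check by formula (change).** The ratio is √(1 + c²·E[D²]/Var[D]), where D is the change without laboratory effects.
- Mean change zero: √(1 + c²) = 1.005, 1.02, 1.04.
- Baseline assumed twice follow-up (in units of mean follow-up): E[D²] = 1.1225 × (1.04 + 4.16 − 4) = 1.347 and Var[D] = 0.347, so E[D²]/Var[D] = 3.88. At c = 20% and 30% the ratio is √1.155 = 1.07 and √1.349 = 1.16.
- Baseline assumed three times follow-up: E[D²] = 1.1225 × (1.04 + 9.36 − 6) = 4.939 and Var[D] = 0.939, so E[D²]/Var[D] = 5.26. The ratio is √1.210 = 1.10 and √1.473 = 1.21.

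**Clotting-time-like test** (assumed mean 13 s, CVs 7% and 4%). At between-laboratory CVs of 0, 5%, 10% and 15% the raw SD is 0.213, 0.248, 0.331 and 0.442 s. The last three are 1.16, 1.55 and 2.08 times the first. The change table stays at about 0.15 s. The relative effect is larger because subjects vary little.

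**The case against.** The case for leaving the plan alone is strong in several respects.

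- **No bias.** A reader might infer that laboratory differences systematically favor or disfavor the 9-mg arm. With 1:1 randomization they do not; only chance imbalance remains, and no hypothesis test is planned on these tables. This stands. The 3-mg column is a separate case: its subjects entered under version 1.0 and may come from a different mix of sites, though the documents do not say so.
- **Change from baseline is already planned.** It removes most of the laboratory effect under favorable conditions. This stands, within limits. Baseline is taken soon after major trauma, so mean change need not be near zero. Standard-of-care results from before consent may serve as screening values, and the documents do not say whether these can come from another laboratory.
- **Other displays exist.** ULN-based PCS criteria, the liver listing and the out-of-range listing cover larger or individual excursions, and INR covers PT. Coagulation is scheduled only at screening and once after surgery. This narrows the gap to GGT, aPTT and moderate enzyme shifts.
- **The size is assumed.** A reader might take a far larger loss from extreme inputs. A between-laboratory CV of 60% with a subject CV of 40% gives an SD ratio of √(1.16 × 1.36 − 1)/0.4 = 1.90, which keeps only 1/1.90² = 28% of the information. Nothing in the documents supports that input, and the figure would apply to raw values only.
- **ULN is an imperfect scale.** Laboratories set limits differently, and limits may depend on age and sex, so scaling adds some variation of its own. This stands, and is a reason to add the scaled tables and not to substitute them.

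**Conclusion.** The point holds as a minor loss of precision in descriptive safety tables. Pooling local-laboratory values with unit conversion alone adds about 5% to 30% to the SD of the raw between-arm difference for an enzyme-like test, at an assumed between-laboratory CV of 10% to 30%. In the change tables the addition is about 0% to 8% with a shared laboratory and mean change near zero. At a CV of 30% it could reach about 16% to 21% if baselines are two to three times follow-up values, or about 40% if 30% of baselines come from another laboratory. Every variability input is an assumption, and the number of laboratories is inferred from the number of sites.

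The documents do not support a claim of bias between 9 mg and placebo, or of any effect on the primary endpoint, power or type I error.

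**What to change.** Keep the SI-unit summaries; removing them would put the SAP in conflict with Protocol 12.3.4.2. Add to SAP 9.4.2, for the final analysis:

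*For ALT, AST, ALP, GGT, total bilirubin, CPK, amylase, lipase and aPTT, each result will also be divided by the ULN of the laboratory that reported it. The scaled value and its change from baseline will be summarized by treatment group and scheduled time point.*

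Dividing by the reporting laboratory's limit also deals with a baseline that comes from a different laboratory. Add a sentence that PT is to be read through the INR summary already planned.

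The cost is SAP wording, programming and a few extra tables. Local limits should already be in the database, because Table 12-4 and the out-of-range listing depend on them. The SAP introduction allows documented revisions before final database lock. It also says that the Section 10.1 interim methods have been carried out, so no change to SAP 10.1.3 is proposed.

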9 STATISTICAL ANALYSIS

9.1 General Considerations

The Schedule of Assessments is provided in [Appendix A](#).

The precision standards for reporting safety and efficacy variables are provided in an internal Biometrics document that specifies the programming rules, including the precision for derived variables.

All individual subject data for subjects who were randomized or received study drug will be presented in individual subject data listings.

Continuous variables will be summarized using the following descriptive summary statistics: the number of subjects (n), mean, SD, standard error (SE), median, minimum value (min), and maximum value (max).

Categorical variables will be summarized using counts and percentages. Percentages will be presented to 1 decimal place unless otherwise specified.

Baseline value, unless otherwise specified, will be defined as the most recent non-missing measurement (scheduled or unscheduled) collected before administration of study drug.

Change (absolute change) from baseline will be calculated as:

Post baseline value - baseline value.

The treatment-emergent (TE) period will include the time from dosing with study drug to the Safety Follow-up Visit or 28 days after treatment / the last available visit (whichever is later) for subjects who do not have a Safety Follow-up Visit.

Unscheduled visits: Unscheduled visit measurements will be included in analysis as follows:

- In scheduled visit windows per specified visit windowing rules.
- In the derivation of baseline measurements
- In the derivation of maximum/minimum values and maximum/minimum changes from baseline values.
- In individual subject data listings as appropriate.

Visit window rules: The analysis visit windows for protocol-defined visits are provided in [Appendix B](#).

Repeated observations within the same visit window:

- For all efficacy parameters, if there are multiple measurements within a visit window, the record at the scheduled visit will be used. If there are no measurements at the scheduled visit, then 1) the record closest to the target day will be used; or 2) if there are multiple records with the same distance to the target day, the latest record will be used.
- For all safety parameters, if there are multiple measurements within a visit window, then 1) the record closest to the target day will be used; or 2) if there are multiple records with the same distance to the target day, the latest record will be used.

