9.4 Safety Analysis

All safety summaries will be based on the set of data associated with the TE period for subjects in the Safety Set.

The overall safety profile of VX-210 will be assessed in terms of the following safety and tolerability endpoints:

- Incidence of treatment-emergent adverse events (TEAEs)
- Clinical laboratory values (i.e., hematology, serum chemistry, coagulation studies, and urinalysis)
- ECGs
- Vital signs

All safety data will be presented in individual subject data listings.

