Neutrophils	<1.5 Giga/L (Non-Black); <1.0 Giga/L (Black)	International Consensus meeting on drug-induced blood cytopenias, 1991. FDA criteria.
Monocytes	>0.7 Giga/L	
Basophils	>0.1 Giga/L	
Eosinophils	>0.5 Giga/L or >ULN (if ULN ≥0.5 Giga/L)	Harrison- Principles of internal Medicine 17th Ed., 2008.
Hemoglobin	≤115 g/L (Male); ≤95 g/L (Female) ≥185 g/L (Male); ≥165 g/L (Female) Decrease from Baseline ≥20 g/L	Criteria based upon decrease from baseline are more relevant than based on absolute value. Other categories for decrease from baseline can be used (≥30 g/L, ≥40 g/L, ≥50 g/L).
RBC	≥6 Tera/L	
Platelets	<100 Giga/L ≥700 Giga/L	International Consensus meeting on drug-induced blood cytopenias, 1991.

Table 12-5 Criteria for Potentially Clinically Significant ECGs

Parameter	PCS	Comments
HR	≤50 bpm and decrease from baseline ≥20 bpm ≥120 bpm and increase from baseline ≥20 bpm	
PR	≥220 ms and increase from baseline ≥20 ms	
QRS	≥120 ms	
QTc	Absolute values (ms)	To be applied to any kind of QT correction formula.
Borderline	Borderline: 431-450 ms (Male); 451-470 ms (Female)	
Prolonged*	Prolonged: >450 ms (Male); >470 ms (Female)	
Additional	≥500 ms	
	Increase from baseline	
	Borderline: Increase from baseline 30-60 ms	
	Prolonged: Increase from baseline >60 ms	

Coagulation

aPPT	≥65 seconds
PT	≥17 seconds
INR	≥1.7

Note: Based on CPMP 1997 guideline.

Table 12-6 Criteria for Potentially Clinically Significant Vital Signs

Parameter	PCS	Comments
HR	≤50 bpm and decrease from baseline ≥20 bpm ≥120 bpm and increase from baseline ≥20 bpm	To be applied for all positions (including missing) except STANDING.
SBP	≤95 mmHg and decrease from baseline ≥20mmHg ≥160 mmHg and increase from baseline ≥20 mmHg	To be applied for all positions (including missing) except STANDING.
DBP	≤45 mmHg and decrease from baseline ≥10 mmHg ≥110 mmHg and increase from baseline ≥10 mmHg	To be applied for all positions (including missing) except STANDING.

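### Laboratory PCS counts take no account of pre-dose status, so persisting trauma abnormalities dilute the between-arm comparison

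*SAP*

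**What the plan says.** SAP 9.4.2 sets the counting rule: "The number and percentage of subjects with at least 1 potentially clinically significant (PCS) event during the TE period will be summarized overall and by" arm. SAP 9.4 fixes the data used: "All safety summaries will be based on the set of data associated with the TE period for subjects in the Safety Set". SAP 9.1 sets the start of the period: "The treatment-emergent (TE) period will include the time from dosing with study drug to the Safety Follow-up Visit or 28 days after treatment", with a later end allowed for subjects who have no Safety Follow-up Visit. Baseline is also defined in 9.1 (it "will be defined as the most recent non-missing measurement (scheduled or unscheduled) collected before administration of study drug"), but 9.4.2 does not use it in the PCS count.

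The limits are in Appendix E, Table 12-4 ("Criteria for Potentially Clinically Significant Laboratory Tests"). Most are absolute values or multiples of ULN: ALT, AST, bilirubin, CPK, glucose, albumin, lymphocytes and platelets, among others. The coagulation limits in the same appendix are absolute as well. Creatinine and hemoglobin have change-from-baseline rows beside their absolute limits, and the comment on hemoglobin reads: "Criteria based upon decrease from baseline are more relevant than based on absolute value".

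Other safety criteria are built differently. The upper heart rate criterion, for example, is "≥120 bpm and increase from baseline ≥20 bpm". PR and blood pressure criteria also combine a limit with a change. A TEAE (SAP 9.4.1) must have arisen or got worse at or after dosing.

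**The concern.** The TE period settles when a value was measured, not whether the abnormality is new. Nothing in SAP 9.1, 9.4.2 or Appendix E sets aside subjects already over a limit, requires worsening, splits the count by baseline status or plans a shift table. The SAP is silent on the matter; it does not expressly decide to include such subjects.

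This population makes the gap matter. Enrollment requires acute traumatic cervical injury with surgery starting within 72 hours (Protocol 9.1). Screening laboratory results may be standard-of-care values taken after the injury (Schedule of Assessments, footnote a), so baseline is itself a trauma value. Intravenous steroids are permitted (Protocol 9.3). Laboratory eligibility rests on the investigator's judgment (Protocol 11.6.2), so a value over a PCS limit does not by itself exclude a subject.

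At stake is how readable the by-arm PCS percentages are. Subjects already over a limit who stay over it are counted in both arms whatever the drug does. With about 50 per arm, a chance difference in how many started over the limit also passes into the table.

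**Working it through.** The plan states no PCS rate, so there is no figure to reproduce. The check is of the counting rule, followed by an illustration of its effect.

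**1. The rule applied to one hypothetical subject.** CPK is 12 × ULN at screening and 11 × ULN at the post-surgery draw. The second value falls in the TE period and exceeds 10 × ULN, so the subject is counted in that row although the value fell. Under a rule built like the heart rate criterion, this subject would not be counted.

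**2. Dilution.** Let p be the share over the limit at baseline and still over it after dosing, taken as equal in both arms. Let r be the rate of new PCS values in the rest.

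Counted rate = p + (1 − p) × r

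Difference in counted rates = (1 − p) × (r₁ − r₀)

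Assumed, not from the documents: r₀ = 10%, r₁ = 30% (difference 20 points, ratio 3.0).

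| p | Counted, arm 0 | Counted, arm 1 | Difference | Ratio |
|---|---|---|---|---|
| 20% | 0.20 + 0.80 × 0.10 = 28% | 0.20 + 0.80 × 0.30 = 44% | 16 points | 1.57 |
| 40% | 0.40 + 0.60 × 0.10 = 46% | 0.40 + 0.60 × 0.30 = 58% | 12 points | 1.26 |
| 60% | 0.60 + 0.40 × 0.10 = 64% | 0.60 + 0.40 × 0.30 = 72% | 8 points | 1.13 |
| 80% | 0.80 + 0.20 × 0.10 = 82% | 0.80 + 0.20 × 0.30 = 86% | 4 points | 1.05 |

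The range is wide because p is unknown and will differ by analyte.

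**3. Chance imbalance.** With 50 per arm (SAP 7.2), the standard error of the between-arm difference in p is √(2p(1 − p)/50):

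- p = 20%: √(2 × 0.16/50) = 8.0 points
- p = 40%: √(2 × 0.24/50) = 9.8 points

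An imbalance d in p moves the counted difference by d × (1 − r). With r = 10%, one standard error gives 8.0 × 0.9 = 7.2 points or 9.8 × 0.9 = 8.8 points. This is sampling noise, not bias, but the baseline data could account for it.

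**4. Cost in denominators.** If every subject over the limit at baseline stays over it, 50 × (1 − p) per arm remain in the at-risk row: 40 at 20%, 25 at 50%, 15 at 70%. As a yardstick of visibility only, take a nominal 2-sided 5% comparison of two proportions with the same 10% v 30%. At p = 20% the power is 38% when everyone is counted (28% v 44%, 50 per arm) and 61% in the at-risk row (40 per arm). At p = 50% it is 17% (55% v 65%) and 42% (25 per arm). On these assumptions the at-risk row shows the contrast better despite fewer subjects.

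**The case against.** The strongest reply is that worsening is already captured elsewhere.

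- Protocol 13.1.1.2 makes a clinically significant worsening from baseline in a laboratory test an AE, and SAP 9.4.1 tabulates TEAEs by arm. That is a by-arm count that leaves out stable or improving abnormalities.
- SAP 9.4.2 summarizes change from baseline by arm at each scheduled time point, where the CPK example would appear as a decrease. It also lists out-of-range values, and liver tests at all visits for subjects with elevated results.
- Graded rows for ALT, AST, CPK, bilirubin, amylase and lipase let a subject who worsens enter a higher category.
- Exclusion criterion 10 and the screening laboratory rule may lower p for some analytes.

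All of this stands as partial cover. The AE route depends on investigator judgment rather than the PCS limits, summaries of change can miss a few large values, and listings give no rate by arm.

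A reader might go further and infer that the tables bias the comparison or hide a drug effect. The documents do not support that: randomization keeps the comparison unbiased on average, no PCS test is planned, and the effect is dilution. Nor do they make the PCS percentages the main laboratory comparison, since SAP 9.4.2 states no order of importance. A reader might also assume high steroid doses, but neither Protocol 5.1.2 nor 9.3 gives a dose. Nor does the SAP always pair a limit with a change outside the laboratory tables: the QRS and absolute QTc criteria have no change condition.

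**Conclusion.** The point holds as a matter of dilution and noise in descriptive safety tables. The risk difference is multiplied by (1 − p), on the assumption that p is equal in both arms. An abnormality present before dosing counts only if it persists into a TE sample; with the first scheduled draw at 24 to 48 hours that is plausible, but its frequency is undocumented. Both p and the 10% v 30% rates are illustrative, so no particular loss can be claimed for this trial. For most analytes, no planned table gives a threshold-based count of new or worsened values by arm. No efficacy endpoint, test or decision rule is affected. The change is worth making because it is cheap and makes the laboratory tables easier to interpret.

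**What to change.** In SAP 9.4.2, tabulate each laboratory PCS criterion by baseline status and arm:

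- One row for subjects who did not meet the criterion at baseline, or were in a lower category, with those subjects as the denominator.
- A separate row for subjects who already met it at baseline, so that nobody drops out of the table.

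A shift table of baseline category by worst TE category, by arm, would serve equally well. State how subjects with no baseline value are shown. Treat QRS and absolute QTc the same way in 9.4.3; QTc already has increase-from-baseline rows, so the gain there is small.

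The cost is SAP wording and one programming condition. Screening chemistry, hematology, coagulation and ECG are already scheduled. SAP 10.1.3 uses the same count, but SAP section 4 says the interim methods have already been carried out, so the change is for the final tables and should be approved before final database lock. Two limits remain: denominators become small where a criterion is often met at baseline, and abnormalities newly caused by the surgery itself still count as new in both arms.
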